3.0 PILOT STUDY

During the school year 2016-17, this project will be pilot tested. One of the main goals is to pilot the implementation of the two intervention models, in addition it will include piloting the measuring instruments and the various tests/examinations. It will also be a test of the logistics with regards to inclusion of participants, collection of data and processing of data, so that when the RCT is rolled out during fall 2017, the actual intervention will have been thoroughly tested. Implementation research suggests that successful implementation of a school-based intervention requires that the researchers include partners at an early stage, and stakeholders (school leaders, teachers, pupils and parents) should be active participants in the development of design, implementation and dissemination of the intervention model.³⁶ Interventions are more likely to be successful when most or all individuals in the setting are committed to the intervention and feel ownership for it. In particular, experience from previous studies shows

better implementation of school-based interventions if the school is committed to the intervention through national, regional and local school policies. Therefore, the pre-planning phase as well as the implementation of the intervention models are an important part of the pilot study.

Six schools in the Oslo area will be included in the pilot study. There is assumingly around 100 pupils in 9th grade at these schools, which means that approximately 600 pupils will be invited to participate. The sample in the pilot study will be a convenience sample. In the pilot study, each intervention model will be tested in two schools (a total of four schools) and two schools will be included as control schools. The two intervention models are planned to be implemented over 16 weeks, and the pupils will be tested both pre- and post-intervention.

4.0 IMPLEMENTATION

According to implementation research, four essential phases are important to achieve a successful implementation of extended physical activity at the lower secondary level.³⁶

1) Pre-planning

This project is initiated and has support from key stakeholders including the Ministry of Education and Research and the Ministry of Health and Care Services. Close cooperation with the aforementioned authorities can give the project group valuable access to established meeting places for dialogue with national, regional and local school policy bodies, the school health service, the parent committee for primary education and school leaders at the selected schools. In addition, the school management must feel committed to participation in the study as they play a crucial role in the successful implementation of health promotion measures both as initiator, and as responsible organizational facilitator.³⁷ The teachers also play a key role in the pre-planning phase.

2) Planning of the program and activities

There will be arranged focus groups with pupils where the aim is to develop an understanding of what preferences they have when it comes to both type of activity and the context where the physical activity should take place. This will ensure pupil participation, and consequently the target group prefers the content of the program. Through information meetings and training of teachers, the aim is to improve adherence to the program from key personnel (principals and teachers).

3) Program delivery

In this phase, the planned program is implemented. It is important to make sure the program is included in the school's curriculum. Teachers are an important factor for program delivery, and training of teachers will be performed. Further, parents are important and they will be invited to information meetings at the school. At these meetings written and oral information about the project will be provided, and they will also be informed of potential risks or discomfort when participating in the study.

4) Monitoring and evaluation of the implemented program

In this phase, the program will continuously be evaluated to assess whether the program work as planned. School leaders and teachers will through logbooks, questionnaires and interviews provide data related to; 1) the extent to which the program and its elements is implemented as planned (fidelity); 2) how much of the program is delivered (dose delivered); 3) how well different program components are delivered (quality); 4) how responsive participants were to the program (responsiveness); and 5) changes made to the program during implementation that enhance its fit with the context (adaptation). Furthermore, parents and pupils will be asked general questions about the school's communication on physical activity and in addition there will be specific questions for participants in the intervention groups about the dosage of the program and the utility value of the various components.

All of these sub-elements will create a common understanding of the premises of the project and thus create a mutual commitment to the implementation of the program. This approach allows a certain degree of local adaptation of the program to ensure implementation, while at the same time there is a need to limit local variation from a research perspective. Good dialogue enables both conditions.

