1.0 INTRODUCTION

As part of creating a better knowledge base for future work on physical activity among adolescents, the "Folkehelsemeldingen - Mestring og muligheter" has defined a trial with a selection of secondary schools where students will receive about four hours of physical activity and physical education during the week.¹ The experiment should be organized so as to best study the effects of increased physical activity (PA) and/or physical education (PE) on the participants physical and mental health, learning and learning environment and, if possible, how it affects the development of PE as a subject.

The main aim of this project is thus defined to find models of PA/PE that can be used in Norwegian lower secondary schools. These models are intended to have an impact on the adolescents' physical health, mental health, learning and learning environment. The fact that the intervention models should affect four different outcomes will make this project very challenging. However, as we face a global trend with increased prevalence and premature deaths caused by non-communicable diseases such as cardiovascular disease, type 2 diabetes, chronic lung disease and cancer this project is timely. Worldwide, these diseases cause two thirds of all deaths and one of four deaths among those below 60 years of age.

Non-communicable diseases are partly due to increased sedentary lifestyle,² and physical inactivity is defined as a significant public health problem for people of all ages.³ Globally, physical inactivity is referred to as one of the four leading causes of mortality.² According to the World health organization, 10% of all deaths in Europe are related to inactivity.⁴ In May 2012, the World Health Assembly (WHA) adopted the target of reducing premature death of non-communicable diseases by 25% by 2025. WHO has identified four overall indicators and targets to reach this target. One of the goals is that the proportion that is physically inactive should be reduced by ten percent.

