2.1 Design

Adolescents in 9th grade will be invited to participate in the study. This is a multi-center study and four universities and colleges in Norway are included (Norwegian School of Sport Sciences, Sogn and Fjordane University College, University of Agder and University of Stavanger). The Norwegian School of Sport Sciences is the coordinating unit.

Schools located in municipalities in the geographical area around the four universities will be invited to participate. This will be a cluster sample with schools as the primary unit. When a school agree to participate, all adolescents in 9th grade will be invited to participate in the study. After inclusion, schools will be randomly allocated to either one of the intervention arms or the control arm. The randomization will be conducted by a neutral third part not affiliated with the project team.

Some schools already arrange for extended time for physical activity during the school day. Schools that already are working systematically with PA or extended PE as an integrated part of their curriculum will be excluded from participation in the study. However, this does not apply to schools that have organized specific events e.g. activity days, school tournaments and mountain hikes.

The project was reviewed by the Regional Committee for Medical and Health Research Ethics (REK) in Norway, who according to the Act on medical and health research (the Health Research Act 2008) concluded that the study did not require full review by REK. We will therefore apply for approval from The Norwegian Social Science Data Services (NSD) for permission to collect personal data. From an ethical point of view, upper secondary school pupils are not able to give valid consent to participation in surveys. We will therefore obtain written consent from the pupils' parents/caregivers before inclusion in the study. Both parents/caregivers and the adolescents will receive information about the goals of the study, any disadvantages or discomfort that may arise, that participation is voluntary and that they may withdraw from the study at any time and without justification.

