The Be Happy lessons are self-organized activity groups of at least three pupils, developed according to activity preferences. In the initial phase of the model, the pupils should, in collaboration with the teachers, discover different activity contexts for the "be happy" lesson. The main aim of this phase is that all pupils should be able to find a desirable activity context. Examples of activity contexts are dance/choreography, traditional sports, outdoor activities, drama, yoga and hiking groups. An activity context should be defined as a group of young people who will develop and exchange interests and values with peers through a clear form of activity during school hours (and possibly beyond school hours). They will develop goals for the activity, as well as both annual and period plans for the activity. The social dimension of friendship in motion should be central in all groups. The "don't worry" lesson should take place within the class (like other PE lessons), but this lesson should be related to the "be happy" activities. The adolescents work individually or in smaller groups with the teacher as support.

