2.3 Outcome measures

All participants will be tested at baseline and at the end of the intervention period. The variables are described below.

In this project, **physical health** is defined as good bodily health achieved through a balance of regular physical activity, ability to perform daily activities with excess and the presence of physiological features and qualities associated with low risk of developing lifestyle diseases and disorders.

- **Physical activity**

Physical activity is the main outcome variable. The participants physical activity level will be assessed by ActiGraph accelerometers (model GT3X+) (ActiGraph, LLC, Pensacola, Florida, USA). The GT3X measures acceleration in three individual plans of motion. ActiGraph accelerometer is widely accepted as a valid and reliable too for measuring physical activity in adolescents.¹⁴⁻¹⁶. Participants will be asked to wear the accelerometer at the right hip for seven consecutive days. Outcomes for physical activity levels are mean physical activity level (counts/min) and time spent in different PA intensities using established cut-offs (sedentary time, light physical activity, moderate physical activity, moderate-to-vigorous physical activity and vigorous physical activity). Further, a questionnaire will be developed to gain information on type of activity that is performed as well as information regarding the activity context.

- **Health-related physical fitness**

Health-related physical fitness is defined as physiological features and qualities that are associated with low risk of development of lifestyle diseases and disorders and include components such as cardiovascular fitness, muscular endurance, muscular strength and body composition.

Cardiorespiratory fitness

Cardiorespiratory fitness is one of the most important components of the term health-related physical fitness and studies clearly shows that individuals with good cardiorespiratory fitness have better physical health compared to those with poorer cardiorespiratory fitness.¹⁷⁻¹⁹

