MENTAL HEALTH concerns whether a person manages to use his cognitive and emotional skills to function in society and meet everyday demands. In research literature, mental health is often related to the chosen goals of mental health. In this study, the aim is to measure mental health by both symptoms of various mental disorders and quality of life that deals with physical and emotional well-being, self-esteem and relationships with family, friends and school. When selecting instruments for measuring mental health, the best instruments for this age group with official Norwegian translations have been chosen.

- **Strength and Difficulties Questionnaire (SDQ)**

The Strength and Difficulties Questionnaire (SDQ) will be used. This is a short screening tool for assessing young people's mental health.²⁸ The instrument has 25 questions and covers five scales (emotional, conduct, hyperactivity, peer problems and prosocial behavior). SDQ has previously been used in both population-based and clinical studies in several countries (Youthinmind) including Norway.^{29,30}

- **Hopkins symptom check list (HSCL)**

Hopkins symptom check list (HSCL) will also be included in the questionnaire. HSCL is considered as a good tool for mental health surveying, and the short version consisting of 10 questions is included (HSCL-10). Each question is answered on a four-part scale: "not bothered", "a little bothered", "quite bothered" and "very bothered". Not bothered gives 1 point, while very bothered gives 4 points, and when the points are summed, a score between 10 and 40 is gained where 40 means very bothered.

- **Quality of life**

KIDSCREEN is a questionnaire that measures health-related quality of life in children and adolescents aged 8-18 years. In this study KIDSCREEN-27 is used that includes five Rasch scaled dimensions: physical well-being, psychological well-being, autonomy & parents, peers & social support and School Environment. The questions are answered on a five-point Likert scale that indicates either the frequency or intensity of a behavior or feeling.³¹ This instrument has also been used in the Active Smarter Kids (ASK) study.²³

- **Self-evaluation of competence or adequacy**

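### The plan describes no recording of physical injury or adverse events in any arm, so injury risk cannot be compared between either model and control

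*Combined protocol and SAP*

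**What the plan says.** The Introduction gives the purpose: "The main aim of this project is thus defined to find models of PA/PE that can be used in Norwegian lower secondary schools". Section 2.2 adds, in both intervention arms, one hour of activity and one physical education lesson each week for a school year. In the first model a teacher leads the activity, with pupil involvement. In the second, "The Be Happy lessons are self-organized activity groups of at least three pupils", and the companion lesson is held in class with teacher support.

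Risk is acknowledged in two places, both as information for families. The consent information in section 2.1 covers "any disadvantages or discomfort that may arise". At the parent meetings in section 4.0 (Program delivery), "they will also be informed of potential risks or discomfort when participating in the study".

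Section 2.3 says "All participants will be tested at baseline and at the end of the intervention period" and lists activity, fitness, anthropometry, mental health, learning and learning environment. Section 2.4 adds questionnaire content on background, activity type, transport, sedentary behaviour, sleep, smoking and alcohol. Monitoring in section 4.0 covers fidelity, dose delivered, quality, responsiveness and adaptation. In addition, "parents and pupils will be asked general questions about the school's communication on physical activity", and for intervention pupils "there will be specific questions for participants in the intervention groups about the dosage of the program and the utility value of the various components". None of these places names injury, pain or adverse events.

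**The concern.** The trial is meant to produce models for general use in schools. Extra physical activity brings extra exposure to injury, and the two models deliver it under different supervision, so injury risk could differ between the models as well as from control. A school authority deciding on adoption would want that comparison beside the benefits. If injuries are not recorded during the trial, the analysis cannot supply them afterwards. Counts gathered informally in intervention schools alone would have no comparator.

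**Working it through.** **Step 1: is injury recorded anywhere?** The plan states no figure for harms, so there is none to reproduce. The check is to read each place where such data could be collected or used.

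| Place in the plan | Injury or adverse events named? |
|---|---|
| 2.1 consent information; 4.0 parent meetings | Risk and discomfort, as information only |
| 2.3 outcomes | No |
| 2.4 questionnaire and testing | No |
| 2.5 analysis | No |
| 3.0 pilot | No |
| 4.0 monitoring (logbooks, interviews, pupil and parent questions) | No |
| 6.0 quality assurance | No |

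The questionnaire, the data collection manual mentioned in section 6.0, and any section 5.0 were not available to read. The finding is therefore that no recording is described, not that none exists.

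**Step 2: which harms can still be seen?** Section 2.3 says "the aim is to measure mental health by both symptoms of various mental disorders and quality of life". The SDQ, HSCL-10, KIDSCREEN-27 and self-perception profile are listed for the trial, as are reading and numeracy. Section 2.5 compares the intervention groups with control at a two-sided 0.05 level, so worsening on these measures would show. Loss in reading or numeracy is a relevant harm, because section 2.2 moves 5% of the remaining school hours to physical education. The gap is physical injury.

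**Step 3: scale of the extra exposure (illustration).** From the plan: one extra hour and one extra lesson a week, and at least 590 pupils per arm. Assumed, because the plan does not give them: 1.75 to 2 extra hours a week in total, 38 school weeks, and 0.1 to 0.5 injuries needing care per 1,000 hours. It is also assumed that the extra time does not displace other activity.

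- Extra pupil-hours per arm: 1.75 × 38 × 590 = 39,235, up to 2 × 38 × 590 = 44,840.
- Extra injuries per arm: 39,235 × 0.1/1,000 = 3.9, up to 44,840 × 0.5/1,000 = 22.4.
- As a share of the arm: 3.9/590 = 0.7%, up to 22.4/590 = 3.8%.

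**Step 4: what could a symmetric item detect?** This is one model against control, two-sided alpha 0.05, 80% power, normal approximation for two proportions, with n divided by the design effect. Control risks are assumed. The factor 1.1 is the plan's (section 2.5); 2.0 is an assumed less favourable value. The table gives the smallest detectable risk in the model arm.

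| Control risk | 590 per arm, 1.1 | 590 per arm, 2.0 | 492 per arm, 1.1 | 492 per arm, 2.0 |
|---|---|---|---|---|
| 2% | 5.2% | 6.7% | 5.6% | 7.35% |
| 5% | 9.45% | 11.3% | 9.95% | 12.05% |
| 10% | 15.75% | 18.0% | 16.35% | 18.9% |
| 20% | 27.3% | 30.0% | 28.0% | 31.0% |

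The 492 is the number per group that section 2.5 wants to examine. A 20% loss from 590 would strictly leave 590 × 0.8 = 472. At 472, with a factor of 1.1, a control risk of 5% gives 10.05% instead of 9.95%, so the choice matters little here.

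**Step 5: precision.** With a true risk of 5% in both arms and 492 per arm, the 95% interval for the difference has half-width 1.96 × √(2 × 0.05 × 0.95 × 1.1/492) = 2.9 percentage points. With a design effect of 2.0 it is 1.96 × √(2 × 0.05 × 0.95 × 2.0/492) = 3.9 points.

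**The case against.** The strongest objection is that the item would not settle the question. The illustrative excess of 0.7 to 3.8 points lies mostly below what the trial could detect: at 492 per arm and a factor of 1.1, the smallest detectable difference is 3.6 points for a 2% control risk and 4.95 points for 5%. This stands. The item would give an estimate and an interval that excludes large increases, not a demonstration of safety. It is also fair that unseen documents, the manual above all, may already deal with reasons for missed tests.

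Four stronger readings are tempting, and the documents do not support them.

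- *The trial can report only benefits.* It cannot be put that way, because mental health, quality of life and academic performance are tested two-sided and can show harm.
- *The gap arises because extra questions go only to intervention pupils.* Those questions concern the dosage and usefulness of a programme that controls do not receive. The asymmetry is natural, and no text says harms would be gathered that way.
- *Injured pupils miss the fitness tests, so fitness results look too good.* The direction is unknown: injured pupils may be the fitter, more active ones, and controls are injured too. The size is small: if all 22 of 590 pupils (3.7%) were missing and averaged 0.5 SD worse (assumed), the arm mean would shift by 0.037 × 0.5 = 0.02 SD. The primary outcome is accelerometer counts, not a performance test.
- *Self-organised groups are the riskier model.* The example activities include yoga, drama and dance as well as sports and hiking, and pupils help lead activity in the first model too. The text shows a difference in delivery, not a ranking of risk.

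**Conclusion.** The concern holds for physical injury and adverse events. The text describes no recording of them in any arm, so injury risk cannot be compared between either model and control, or between the two models. The primary analysis is unaffected, and the other harms that the plan measures remain visible. This is a low-cost improvement, not a flaw that undermines the trial.

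The size of the missing information is uncertain. About 4 to 22 extra injuries per arm follows from assumed lesson time, weeks and rates, and should be read only as an order of magnitude. A symmetric item could inform on common injuries: at 492 per arm it would detect roughly a 1.4-fold increase (control risk 20%, factor 1.1) to a 3.7-fold increase (control risk 2%, design effect 2.0). It could not inform on rare serious injuries. The conclusion rests on the text that was available; the questionnaire or manual could narrow it.

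**What to change.** 1. Add one item to the post-test electronic questionnaire, with the same wording and recall period in all three arms: any injury during the school year that led to medical care or to missed physical education or activity, and where it happened (physical education, project lesson, other school time, leisure).
2. Have testers code the reason for each missed post-test (injury, illness, absence, refusal), if the data collection manual does not already require it.
3. Report both by arm beside the benefit outcomes, with confidence intervals that allow for clustering by school.
4. State in section 2.5 that about 590 pupils per arm (about 492 examined after drop-out) can inform on common injuries but not on rare serious ones.

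The 2016-17 pilot, which already tests the instruments and includes two control schools, is a convenient place to try the wording. The cost is about a minute per pupil, recall error over a school year, and one extra code when a test is missed. No extra visits or staff are needed, because the questionnaire and test teams are already planned.
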